Accuracy of computer-assisted template-based implant placement using CAD/CAM stereolithographic surgical templates with or without metallic sleeves: a randomized controlled trial

[name]

Randomization

One computer-generated restricted randomization list was created. Only one of the investigators, not involved in the selection and treatment of the patients, was aware of the random sequence and could have access to the randomization lists stored in a password-protected portable computer. The random codes were enclosed in sequentially numbered, identical, opaque, sealed envelopes. Envelopes were opened sequentially after the prosthetic-driven plan was approved.

Statistical analysis

Patient data were collected in a Numbers spreadsheet (Version 3.6.1 for Mac OS X 10.11.4). A bio-statistician with expertise in dentistry analyzed the data using SPSS software for Mac OS X (version 22.0; SPSS Inc., Chicago, IL, USA) for statistical analysis. Descriptive analysis was performed for numeric parameters using mean \pm standard deviation and median with confidence interval (95% CI). Implant failure and template-related complications between the two groups were compared using Fisher's exact probability test. The mean differences of the overall deviation in the clinical outcomes compared to the virtual plan, were compared between groups using a mixed-model repeated-measures analysis of variance (ANOVA). In the sleeve-less group, accuracy of open versus closed holes were also evaluated. All statistical comparisons were conducted with a P value set at 0.05.

Results

Thirty-two patients were considered eligible for this trial. Two patient was not included due to them not wanting to participate in this study. No patient dropped out, and all patients were treated according to the allocated interventions.

Fifteen patients (8 female and 7 male with a mean age of 45.1 years) were randomised to the control group (template with metallic sleeves) and 15 (10 female and 5 male with a mean age of 55.2 years) to the test group (without metallic sleeves). A total of 37 implants were placed in the control group while 43 implants were placed in the test group. Of these, 12 implants were placed through open sleeves and 31 through closed sleeves.

No implants failed and no complications were experienced. All the implants were inserted according to the manufacturer's instructions, with an insertion torque ranged between 35 an 45 Ncm.

	Conventional (n=29)	Digital (n=28)	P value
Age	45.4±13	43.7±15.7	0.795
Female patients	5	6	1
Implants placed in the maxilla	18	15	0.596
Immediately loaded i plants	13	11	0.790
Post-extractive implants	4	1	0.352
Sinus lift procedures	2	1	1
Complete restorations	3	1	0.611
Partial restorations	3	2	1
Single restorations	7	18	0.003

1.

|

|

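### Table 1 describes other arms, patients and implants than this trial's, so its balance statements and P values say nothing about the sleeve and sleeve-less groups

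*SAP*

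**What the plan says.** The title sets the comparison: "surgical templates with or without metallic sleeves: a randomized controlled trial". The Results section of the SAP then describes the two groups in the text:

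- Control (metallic sleeves): "Fifteen patients (8 female and 7 male with a mean age of 45.1 years) were randomised to the control group".
- Test (sleeve-less): "15 (10 female and 5 male with a mean age of 55.2 years) to the test group".
- Implants: "A total of 37 implants were placed in the control group while 43 implants were placed in the test group". The 43 test implants are split into 12 through open and 31 through closed holes.

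No standard deviation accompanies either mean age.

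Table 1, captioned as the main patient and implant characteristics, has other columns: "Conventional (n=29" and Digital (n=28). It gives ages of 45.4±13 and 43.7±15.7 (P = 0.795), and the row "Female patients" shows 5 and 6. Its other rows cover jaw, immediate loading, post-extraction implants, sinus lifts and restoration type. The row "Single restorations" shows 7 and 18 (P = 0.003). No sleeve group and no open or closed hole appears in it.

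**The concern.** A characteristics table lets the reader judge whether two small randomised groups are alike in what might affect the outcome. With 15 patients per arm, chance differences in jaw, extraction socket or type of restoration are a plausible rival explanation for a difference in accuracy. The SAP reports such differences: P = 0.0063 for angle and P = 0.0126 for the vertical plane, from comparing the control group with only the closed-hole implants of the test group. That is a subset comparison, so case mix deserves particular attention.

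If Table 1 belongs to other patients, a reader who relies on it draws two wrong conclusions: that age is balanced, and that single restorations are not. The reader also has no valid table of site characteristics against which to judge the accuracy comparison.

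**Working it through.** **1. The two descriptions side by side** (SAP, Results text, against SAP, Table 1)

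| Item | Results text | Table 1 |
|---|---|---|
| Arms | metallic sleeves v sleeve-less | Conventional v Digital |
| Implants | 37 + 43 = 80 | 29 + 28 = 57 (see step 2) |
| Women | 8 + 10 = 18 | 5 + 6 = 11 |
| Mean age | 45.1 v 55.2 | 45.4 v 43.7 |
| Age gap | 55.2 − 45.1 = 10.1 years | 45.4 − 43.7 = 1.7 years |

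The one near match is 45.1 against 45.4. The other mean age, the sex counts, the denominators and the arm names all disagree.

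**2. Reproducing the count rows.** The method is a two-sided Fisher's exact test on a/n v b/m, which sums the hypergeometric probabilities of all tables no more likely than the observed one. It was run with Table 1's denominators and then with this trial's implant numbers.

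| Row | Counts | Printed P | At 29/28 | At 37/43 |
|---|---|---|---|---|
| Maxilla | 18 v 15 | 0.596 | 0.596 | 0.258 |
| Immediately loaded | 13 v 11 | 0.790 | 0.790 | 0.464 |
| Post-extraction | 4 v 1 | 0.352 | 0.352 | 0.176 |
| Sinus lift | 2 v 1 | 1 | 1.0 | 0.593 |
| Complete restorations | 3 v 1 | 0.611 | 0.611 | 0.331 |
| Partial restorations | 3 v 2 | 1 | 1.0 | 0.658 |
| Single restorations | 7 v 18 | 0.003 | 0.003 | 0.032 |

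All seven agree at 29/28 and none at 37/43. The figures 29 and 28 therefore served as the denominators for the implant rows and are best read as implant counts.

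**3. Reproducing the age row.** The method is a pooled two-sample t-test, t = (45.4 − 43.7) / [s·√(1/n + 1/m)]. For equal groups, s = √[(13² + 15.7²)/2] = √207.7 = 14.41.

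- 15 v 15: t = 1.7 / (14.41 × √(2/15)) = 1.7 / 5.26 = 0.323 on 28 df, P = 0.749.
- 10 v 10: t = 1.7 / (14.41 × √(2/10)) = 1.7 / 6.45 = 0.264 on 18 df, P = 0.795.
- 29 v 28: P = 0.657.

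The printed 0.795 does not arise at this trial's 15 v 15. It arises at 10 v 10, but also at a few unequal splits such as 9 v 12 and 12 v 8.

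**4. The sex row.** Women 5 v 6 gives P = 1 at 10 v 10, at 9 v 12 and at 15 v 15, so this P value does not discriminate. The counts do: 11 women cannot be the 18 in the text.

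Table 1 is thus coherent for a data set of 57 implants in fewer patients than this trial's 30. Relabelling its columns would not turn it into a table of this trial's 80 implants.

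**The case against.** The strongest case on the other side grants the mismatch and limits what follows from it. Most of that case stands.

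- **Concealment.** A reader might infer that the table conceals the age gap. It does not: both means are printed by arm in the Results text. The table contradicts them.
- **No baseline information.** A reader might infer that the sleeve arms are not described at all. The text gives mean age and sex by arm, and the open and closed split. What is absent is an age SD and the implant-level items.
- **Significance of the age gap.** A reader might call the 10.1 years statistically significant. Without an SD for these arms this cannot be settled. Assuming a common SD of 10 to 18 years, the gap is 1.01 to 0.56 SD and the t-test P runs from 0.010 to 0.136, across 0.05. A baseline significance test after randomisation tells little in any case.
- **Effect on the accuracy results.** A reader might infer that the reported differences are confounded or invalid. Nothing in the SAP links age to template accuracy. The mixed-model ANOVA it names lists no baseline covariates, and the accuracy figures disagree with nothing in Table 1. This is an error in the document, and correcting it changes no reported estimate.
- **Source of the table.** The SAP's Conclusions speak of intraoral digital impressions, and its reference list includes an accuracy trial of conventional against digital impressions. That suggests carry-over from that work, but the SAP does not say so, and it remains an inference.

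One possible defence fails. Faulty reading of the PDF cannot explain the mismatch, because the table's P values agree with its own counts and denominators.

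**Conclusion.** Table 1 does not describe this trial. The arm names, implant totals (57 against 80), numbers of women (11 against 18) and mean ages disagree with the Results text. The reproduced P values rule out a mere slip in the headings: seven of seven match at 29/28, none at 37/43, and the age P is 0.749 rather than 0.795 at 15 v 15. This rests on Fisher's exact test and a pooled t-test having been used for the table, an assumption that the exact agreement supports.

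Two statements must therefore be withdrawn: the 1.7-year age gap with P = 0.795, and the single-restoration imbalance with P = 0.003. The figure that belongs to this trial is a 10.1-year difference in mean age. Its standardised size is unknown until the SDs are given. Valid data on jaw, post-extraction site, loading and restoration type are not shown for the 80 implants. Because this is the only characteristics table in the document, it has to be corrected. The finding does not extend to the validity of the accuracy estimates.

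**What to change.** Delete Table 1 together with its P values. In its place, under the headings metallic sleeves and sleeve-less, give:

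- for the 15 + 15 randomised patients: age with SD, and sex;
- for the 37 + 43 implants: jaw, post-extraction site, immediate loading, sinus lift and restoration type, as far as these were recorded, plus open or closed hole.

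State the mean ages of 45.1 and 55.2 years, a difference of 10.1 years, as a limitation, without a baseline significance test. A sensitivity analysis adjusted for age is optional. It would be a post-hoc choice with 15 patients per arm and should be labelled so. The Conclusions on digital impressions should be checked at the same time.

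The cost is one re-tabulation, provided the site items were recorded for these implants, which the SAP does not show. Any item that was not recorded should be named as unavailable. The arms will look less balanced on age than Table 1 suggests.
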